5.4 RSV Study schedule of endpoints & procedures

The table below summarizes the study endpoint assessments and procedures for RSVs.

Table 2. RSV Study Procedures

	RSV Month 3	RSV Month 6	Month 9	RSV Month 12	Week 54 ^λ
RSV Visit #	2	3		4	
Telephone Call #			1		2
Day# (from Baseline)*	90 ± 14	182 ± 14	272 ± 14	365 ± 14	380 ± 7
History and physical exam					
Interim medical history	X	X	X	X	X
Symptom assessment	X	X	X	X	X
Concomitant Medications review	X	X	X	X	X
Abbreviated Vital signs	X	X		X	
Abbreviated Physical exam**	X	X		X	
WHO functional class**	X	X		X	
Testing					
Phlebotomy: NT-proBNP, sex hormones and other research labs)	X ¹	X ²		X ³	
DXA				X ⁴	
Remote Six minute walk test	X	X		X	
Six minute walk test in-clinic	X ¹	X ²		X ³	
SF-36, emPHasis-10	X	X		X	
Echocardiogram		X ²		X ³	
Actigraphy & Activity Diary	X	X		X	
Urine collection		X ²			
Study procedures					
Dispense study drug/placebo & vitamin supplements		X		X ⁵	
Adverse events	X	X	X	X	X
Medication compliance	X	X	X	X	

* Screening and Baseline visits will not be performed remotely.

**To be done before remote six minute walk test.

λWeek 54 Follow-up telephone call should be completed 7-10 days after the last study assessment.

¹Collected within 8 weeks of RSV.

²Collected within 12 weeks of RSV.

³Collected within 16 weeks of RSV.

⁴Collected within 16 weeks but can be collected outside of 16 weeks.

⁵Up to an additional 42 pills may be dispensed if subject qualifies for study drug extension

5.5 Subjects' retention and drug compliance

We will enforce subject retention in several ways. We will record extensive contact information for each subject at their enrollment in the trial. This will include home, work, and cellular telephone numbers. The research coordinator will call before each study visit to remind the subject to attend. Subjects will be reimbursed for time at the clinic for research procedures for their participation in the study. Subjects will receive \$50 for the Screening Visit, \$200 for the Baseline Visit (\$150 for the visit and \$50 for returning actigraph equipment/diary) and \$250 (\$200 each visit and \$50 for returning actigraph equipment/diary at each visit) for the remaining study visits (month 3, month 6, and month 12) for a total of \$1000. Subjects may also receive additional reimbursement for travel expenses (e.g., hotel room and rideshares/taxis to make study visits).

During RSVs, subjects will be compensated as follows:

- Visit 2 (Month 3) there will be no change in compensation (\$200 for completion of visit and \$50 for returning the actigraph equipment/diary) regardless of whether or not subject returns to center for research blood and 6MWT
- Visit 3 (Month 6)- \$100 for completing the remote visit, \$100 for returning to the center to complete in-person assessments (echocardiogram, 6MWT, research blood, urine)
- Visit 4 (Month 12)- \$100 for completing the remote visit, \$100 for returning to the center to complete in-person assessments (echocardiogram, 6MWT, research blood, DXA scan)

Subjects will be encouraged to attend all study visits at each visit. The research coordinator and physician will explain the importance of compliance with the study protocol at each subject contact. If a subject fails to comply with a study visit, the coordinator will contact him or her by telephone. If this fails, the coordinator will send two letters, one week apart, to request follow-up.

We have considered how to minimize nonadherence with therapy. We will strongly emphasize the importance of complying with the study drug treatment. Nonetheless, we will perform pill counts at visits and record episodes when medication is withheld for any reason.

Chapter 6. Assessment of Efficacy and Outcome Measures

6.1 Assessments of efficacy

Primary

The primary objectives of this study are to assess the effects of AN vs. placebo on the 6MWD at six months (primary end point) and to assess safety and side effects up to twelve months in pulmonary arterial hypertension (PAH).

Secondary

There are several secondary objectives of this study. They include:

- To assess the effect of AN vs. placebo on 6MWD at additional time points (three months and twelve months).
- To assess the effect of AN vs. placebo on RV function (TAPSE, and other measures) at six months and twelve months.
- To assess the effect of AN vs. placebo on plasma NT-proBNP level and other biomarkers at three months, six months and twelve months.
- To assess the effect of AN vs. placebo on SF36 and emPHasis-10 at three months, six months and twelve months.
- To assess the effect of AN vs. placebo on actigraphy-measured physical activity at three months, six months and twelve months.
- To assess the effect of AN vs. placebo on TTCW at twelve months.
- To assess the effect of AN vs. placebo on bone mineral density at twelve months.

6.1.1 Six minute walk distance

Walking is the most basic form of exercise and is integral to daily activities. The 6MWT is a standardized, timed submaximal test of unencouraged, self-determined distance walked which is reliable and valid.(10, 11) Standardized test methods and scripted and timed statements have been established in prior studies of PAH and will be used.(8, 12, 13)

The 6MWT will be performed at baseline, 3 months, 6 months and 12 months. The subject will be instructed to wear comfortable clothing and shoes. The test will be performed at approximately the same time of day at each visit. The Borg score for dyspnea and overall fatigue, oxygen saturation, and heart rate will be recorded at the beginning and conclusion of each test.

For RSVs, the subject will perform the 6MWT with the aid of the coordinator and a family member or friend. Remote walks will only be done if a subject receives clearance from the PI, the study team has confirmed that the walk area is appropriate, and the subject has a companion to help administer the test. A chair will be utilized if needed to sit during or after the walk. The subject will remove the actigraph during a remote 6MWT (if it is being worn). A wearable device (“wristwatch” supplied by the study team) may be worn to track distance during the 6MWT. When study visits resume at local centers after restrictions are lifted, subjects who performed remote 6MWTs will

also perform a 6MWT in-person at the clinic so that the remote data may be harmonized at the end of the study.

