5.1.5 Study Day – Visit 3 (Month 6 ± 14 days)

The research coordinator will ship the actigraph and activity diary to the subject and call the subject 12 days before the visit (and 7 days before the visit) as a reminder to start wearing the actigraph 7 days before the visit and will call again 1-2 days before the visit as a reminder. The coordinator will instruct the subject to not eat or drink (except water) and to avoid heavy exercise for 12 hours before the study day assessment. The coordinator will also request that the subject refrain from smoking for 12 hours prior to the study visit. Subjects will be instructed to take their routine medications on the

morning of the visit and to bring any new medications, study drug, a snack, the actigraph and activity diary with them to the visit.

The subject will arrive at the study site outpatient facility. The following procedures will be performed:

- Complete SF-36, emPHasis-10
- Phlebotomy/Research laboratories
- Urine collection
- Eat a small snack
- Interim medical history/symptom assessment
- Vital signs
- Review current medications
- WHO functional class assessment
- Physical exam
- Study drug accountability
- Dispense study drug & vitamin D supplement and reinforce instructions
- Six minute walk testing with Borg scores
- Echocardiogram
- Collect actigraph and activity diary
- Reinforce instructions on recording of new medications
- Reinforce instructions on bringing the subject's routine and study medications to the follow-up visit
- Reinforce instructions on actigraphy use and activity diary completion

The subject will complete the SF36 and emPHasis-10 questionnaires. Urine sample and blood samples for study assays will be processed and banked at site for later shipment. After the fasting research blood sample is obtained, the subject will be given the opportunity to eat a small snack.

The investigator or research coordinator will take an interim history and perform a physical examination including vitals, review current medications, perform a pill count, dispense a new bottle of study medication, and assess side effects.

The subject will perform the 6MWT. Echocardiography will be performed.

The research coordinator will thank the subject for their attendance and reinforce compliance with the study medication and protocol.

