The subject can perform the 6MWT any day during the visit window following the PI assessment. The subject will schedule the 6MWT with the research coordinator to aid in executing the remote walk. The subject must have a companion that can assist with the remote walk in order for the remote walk to be performed. A wearable device ("wristwatch") utilizing the Global Positioning System (GPS) to record distance may be supplied to be worn during the walk test along with a downloadable application for a smartphone. Subjects who perform a remote walk will also be scheduled to do an in-person six minute walk test if restrictions in place are lifted within the visit window.

During the RSV:

- Review SF-36, emPHasis-10
- Review current medications
- Abbreviated vital signs
- Review of adverse events
- Study drug accountability
- Review the actigraph and activity diary
- Reinforce instructions on recording of new medications and dose changes

- Reinforce instructions on how to take study medication and to not throw away any empty/used medication bottles
- Review instructions for 6MWT, if not already performed

The study coordinator will call the subject at the scheduled time. The subject will complete the SF-36 and emPHasis-10 questionnaires on the same day as the phone call. The study coordinator will review answers to questionnaires and enter data in the database. If the questionnaires were not completed, the research coordinator may also administer the questionnaires over the phone.

The research coordinator will take an interim medical history, review current medications, perform a pill count with the subject counting the number of pills left in the bottle, and assess side effects. Study drug will be shipped directly to the subject when needed.

The research coordinator will have the subject assess vital signs using the study-provided pulse oximeter and blood pressure cuff if available. The subject will weigh himself or herself. The values will be read (or shown if videoconferencing) to the coordinator and recorded.

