The research coordinator will schedule an in-person visit at the center if the center is re-opening within the allowable visit window. The research blood draw, echocardiography, six minute walk test, and DXA will be done in-person. A visiting health service may be utilized to collect research blood and/or urine if the subject agrees. The research coordinator will thank the subject for their compliance with the RSV and reinforce compliance with the study medication and protocol.

Study Drug for Remote Study Visits

Study drug and Vitamin D may be mailed to subjects if an in-person 6 Month Visit cannot be scheduled.

Additional study drug up to six weeks (42 pills) and vitamin D may be mailed to subjects at the 12 Month Visit if an in-person visit can be scheduled within 16 weeks of the Visit 4 study window due to the center re-opening for subject visits.

Week 54 Phone Call

The Week 54 Phone Call should be completed 7-10 days after the last study assessment that is scheduled for the RSV Month 12 Visit.

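### Does the plan need a rule for which walk is the six-month 6MWD when the Month 6 visit is done remotely?

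*Combined protocol and SAP*

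**What the plan says.** Section 5.4, Table 2, places the remote Month 6 visit at day 182 ± 14. It has one row for a remote walk and another for a walk in clinic. A footnote allows the Month 6 clinic walk up to 12 weeks after the remote visit.

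Section 5.3 describes timing in three places:

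- For the home walk: "The subject can perform the 6MWT any day during the visit window following the PI assessment".
- Subjects who walk at home are also booked for an "in-person six minute walk test if restrictions in place are lifted within the visit window".
- The coordinator is to "schedule an in-person visit at the center if the center is re-opening within the allowable visit window". The next sentence reads: "The research blood draw, echocardiography, six minute walk test, and DXA will be done in-person".

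Section 6.1.1 times the clinic walk differently: "When study visits resume at local centers after restrictions are lifted", remote walkers will "also perform a 6MWT in-person at the clinic so that the remote data may be harmonized at the end of the study". It also restricts home walks: "Remote walks will only be done if a subject receives clearance from the PI", and only with a suitable area and a companion.

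Section 7.3.3 compares change in 6MWD between arms by linear regression, adjusted for baseline 6MWD and sex. Section 7.3.1 puts every randomized subject in the intent-to-treat analysis. Section 7.3.4 mentions longitudinal models as something to be considered. None of these refers to remote walks.

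**The concern.** A subject with a remote Month 6 visit could have a raw home distance, a harmonised home distance, or a clinic distance measured around month 9. Nothing fixes in advance which one enters the primary regression. Nor does the plan say what happens when only a late clinic walk exists. That case is foreseeable, because home walks need clearance and a companion.

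The timing texts also seem to disagree. Table 2 gives 12 weeks, Section 5.3 refers to the visit window, and Section 6.1.1 sets no limit. At stake would be an ambiguous primary endpoint, with room to choose among values after the data are known.

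**Working it through.** **1. Do the timing texts conflict?** In Section 5.3 the home walk may fall on any day of the visit window, so that window is most naturally the ± 14 days and not a period counted from the remote visit. The condition on the clinic walk, however, dates the lifting of restrictions and not the walk itself. It requires a booking in one situation and does not forbid a later walk. A site can book whenever restrictions lift in the window and still treat 12 weeks as the outer limit. Section 6.1.1 can be read alongside Table 2. The phrase about an allowable window is undefined and fits either reading. Section 5.5 pays for a Month 6 return that includes the walk, with no ± 14-day limit. The result is loose wording that can be followed.

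**2. How late can the clinic walk be?** Latest day = day of remote visit + 84.

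| Remote visit on day | Latest clinic walk |
|---|---|
| 168 | 168 + 84 = 252 |
| 182 | 182 + 84 = 266 |
| 196 | 196 + 84 = 280 |

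The Month 9 call is at 272 ± 14, days 258 to 286, so the last two fall inside it.

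**3. Precision implied by the plan.** Section 7.4 gives 84 subjects, 10% loss and a 22 m difference at two-sided 0.05; the Protocol Summary gives 80% power. No SD is stated, so 84 cannot be reproduced forward. Evaluable per arm = 42 × 0.9 = 37.8. Solving back gives an SD of 34.1 m by the normal approximation, or 33.7 m by the non-central t. As a consistency check, an SD of 34 m needs 38 per arm, and 76 / 0.9 = 84.4, so 85 in total. Standard error of the arm difference = 33.7 × √(2/37.8) = 7.75 m.

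**4. Late walks counted as six-month values.** Shift = share affected × change in the treatment effect between day 182 and day 266.

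- Flat effect: 0 m.
- Straight-line growth to 22 m at day 182 and beyond (assumed): 22 × 84/182 = 10.2 m more at day 266. For assumed shares of 10%, 20% and 30% the shift is 1.0, 2.0 and 3.0 m. The largest is 3.0/7.75 = 0.39 of a standard error.
- A waning effect would reverse the sign.

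The pilot in Section 1.3 shows median changes of +26 and −12 m at 12 weeks. That gap of 38 m already exceeds 22 m, so it gives no support for continued growth.

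**5. Harmonising on pairs taken far apart.** Any drift between the two walks would be absorbed into a calibration pooled over arms. It would then affect the arm comparison only through chance imbalance in the remote share. At an assumed 20% remote, the SD of that imbalance = √(2 × 0.2 × 0.8 / 37.8) = 0.092. A rough gauge of drift is (26 − 12)/2 = +7 m, which averages two medians. Error SD = 0.092 × 7 = 0.64 m. With a drift of 26 m it is 0.092 × 26 = 2.39 m. These raise the 7.75 m standard error by 0.3% and 4.7%.

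**6. Keep or drop home-only walks?** Power by the normal approximation, with SD 34.1 m and 80% at the start. Keeping uses √(34.1² + f·e²), where f is the remote share and e the extra home-walk SD. Dropping uses 37.8 × (1 − f) per arm. Both f and e are assumed.

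| Share f | Drop | Keep, e = 15 m | Keep, e = 30 m | Keep, e = 45 m |
|---|---|---|---|---|
| 10% | 76% | 79% | 77% | 73% |
| 25% | 68% | 78% | 73% | 65% |
| 50% | 51% | 76% | 66% | 54% |

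Keeping usually wins, but at shares of 10% and 25% it loses when home walks are very noisy. The better rule depends on a quantity that only the paired walks can show.

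**The case for a change.** The strongest case for a change is that this is the primary endpoint and a rule costs only wording. Section 2.2 says six months was chosen deliberately, to limit missing data from deaths, so a value near month 9 is not what was meant. Section 5.3, in discussing extra drug at Month 12, speaks of 16 weeks from the Visit 4 window, so the authors did distinguish a window from an extended period. A concrete case shows the mismatch. With a remote visit on day 182 and restrictions lifted on day 210, Section 5.3 prompts no clinic walk, while Table 2 allows one to day 266.

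What stands: the documents name no six-month value for remote subjects, give no harmonisation method, and word the timing inconsistently.

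What does not stand is the step to a defect that needs correcting. In the day-210 case nothing forbids the later walk. Section 6.1.1, the section on the endpoint itself, gives the clinic walk a calibrating purpose, which implies that the home walk serves as visit data. A month-9 walk as the six-month value is the weaker reading.

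A fixed rule would also have costs. Baseline is always in clinic, so making the raw home distance primary carries any home–clinic difference into the change score and demotes the intended harmonisation. Preferring the clinic walk gives up timing. A longitudinal model needs decisions on the shape of time and on a home–clinic term, which brings analyst choice back.

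**Conclusion.** No change follows. The plan omits a detail that masked analysts can supply sensibly before unblinding, and it was written for visits disrupted by the pandemic. Section 4.5 keeps study personnel and subjects masked until the last follow-up is complete. With randomisation, this limits bias between arms, provided the choice of walk and any calibration are made by masked staff and pooled over arms.

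The illustrative sizes are small: 0 to 3.0 m from late walks, and 0.64 to 2.39 m of added error from calibration, against a standard error of 7.75 m. They rest on an assumed remote share, an assumed time course and an SD solved back from the power statement. Any loss of power from noisy home walks comes from remote measurement itself and not from the absence of a rule. The differing phrases on timing are a matter of tidy wording, and the choice among raw, harmonised and late clinic values is a fair trade-off for the sponsor.

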6.2 Secondary outcome measures

6.2.1 Echocardiographic measures

We will assess right ventricular function (TAPSE) and other parameters as secondary endpoints. The ultimate determinant of outcome in subjects with PAH is right ventricular function, so we have focused on metrics which are predictors of survival in PAH, including RV strain and qualitative RV function.

6.2.2 Plasma NT-pro BNP and other biomarkers

Plasma NT-proBNP reflects right ventricular function in PAH and is a very strong predictor of outcome in PAH. This biomarker will be assessed at baseline, 3 months, 6 months and 12 months. For participants completing RSVs, these biomarkers will be collected within the specified timeframe. Sex hormones and other biomarkers will be assessed at the same time points.

6.2.4 WHO functional class

The WHO functional classification for PAH has been modified from the well-known New York Heart Association functional classification. This functional classification is based on symptoms, with Class I being defined by no symptoms, Class II as having mild limitation in physical activity, Class III as having markedly limited physical activity and Class IV as being unable to perform any physical activity. The WHO functional class will be assessed at every visit.

6.2.5 Actigraphy

Actigraphy is actually a direct measure of physical activity in subjects' day-to-day lives. Actigraphy (or accelerometry) measures the amplitude and frequency of acceleration and

is particularly good at measuring locomotor movement, which comprises the bulk of activities for adults. Physical activity will be measured using the ActiGraph GT9X™ monitor, a lightweight device that contains a rechargeable lithium battery with a recording capacity of approximately 16 days. The device is water resistant with sustained performance after submersion at 1 meter for up to 30 minutes. All three axes provide activity counts to compute a composite vector magnitude (VM). Initialization and data download will be performed using the Actigraph software (Pensacola, FL).

Subjects will begin wearing the device on the day after the baseline visit and will wear it for one week, and for one week periods before the three month, six month, and 12 month visits. Subjects will also complete an activity diary during the week of recording including the date and day of each week with hours of the day. Subjects will indicate when they are asleep, consumption of caffeine, medication administration and when they performed intentional exercise by marking this on the activity diary. Actigraphs and activity diaries from the baseline visit will be shipped (using materials provided) back to the local study centers for data download after a week of wear. For other visits, the actigraph will be shipped to the subject and the subject will bring the actigraph with him/her to the study visit.

6.2.6 Time-to-clinical worsening

We hypothesize that AN will increase the TTCW compared to placebo over twelve months. TTCW is predicated on clinical events which are clearly meaningful (and undesirable) to subjects and clinicians (including starting parenteral therapy, hospitalization, lung transplantation, death). This will be defined as the addition of new PAH therapies or dose increases in previously stable PAH therapy for increased symptoms, hospitalization for PAH progression and/or right-sided heart failure, lung transplantation, atrial septostomy, and cardiovascular and all-cause death.

At each assessment, subjects will be questioned about hospital admissions during the period since their last clinic visit. Families and physicians of subjects who die during the study period will be interviewed by telephone. Research coordinators will obtain hospital records, discharge summaries, and death certificates, which will be reviewed by an expert panel of three external physicians masked to treatment assignment.

Addition of PAH medication or increased doses of current PAH therapies

The addition of new therapy for PAH indicates disease worsening (or subsequent) right heart failure. New PAH-specific medications added to the subjects' medical regimen and the dates when added will be recorded during the study. Often, specific PAH medications which are administered at a stable dose have increased dosing with clinical worsening (specifically, prostacyclin analog therapy). All dose changes will therefore be recorded.

Hospitalization for PAH progression or right-sided heart failure

A hospital admission due to PAH progression and/or right-sided heart failure will be defined as a hospitalization because of lower extremity edema or dyspnea and/or PAH symptoms (e.g., syncope) refractory to outpatient increases in dose or frequency of diuretics or specific PAH medications.

We will record all hospitalizations during the time of the study. Records from each hospitalization will be obtained by the local study coordinator. These records will be reviewed by an independent panel of three physicians who are unrelated to the study.

Cardiovascular death

We will define a cardiovascular death as:

- 1) Sudden death
or
- 2) Death preceded by:
 - a) cardiogenic shock (hypotension resulting in a failure to maintain normal renal or cerebral function for >15 minutes prior to death)
or
 - b) heart failure symptoms or signs requiring:
 - i) intravenous therapy or oxygen in the hospital or
 - ii) confinement to bed

in the absence of secondary causes (such as systemic infection or dysfunction of intravenous or subcutaneous medication delivery devices) or alternative causes of death.

Non-cardiovascular death

A death which does not meet the criteria above will be considered a non-cardiovascular death.

